## BACKGROUND

Chronic Obstructive Pulmonary Disease (COPD) results in nearly 750,000 hospitalizations annually and is the third leading cause of “early” (within 30-day) hospital readmissions in the United States. Curbing preventable early readmissions for acute exacerbations of COPD (AECOPD) has become a national priority, as demonstrated by the Medicare Hospital Readmissions Reduction financial penalty program. One critical barrier in assessing readmission risk is the lack of an easily-measured ‘vital sign’ for COPD: accurate, timely measurements of lung function. Unlike other medical problems that have validated, easily-obtained measurements of organ function, COPD evaluation often defaults to patient report and physician evaluation without critical physiologic data. This lack of objective pulmonary function data during AECOPD in turn leads to critical errors in disease severity assessment. However, the required, repeated measurements by spirometry that can demonstrate responses to therapy can be time-consuming and expensive to perform in a laboratory, and both equipment and staffing infrastructure for bedside testing is cumbersome and often not prioritized. For these reasons, spirometry frequently is not done for patients with AECOPD.

To monitor patient responses to therapy and to assess risks based on objective measures, we propose to the study the use of a portable, patient-driven device (“SpiroPD”) that can be used in both in-patient and outpatient settings, and that reports (via the internet) values collected in real time. While the device has been used in the lung transplant community and for patients with cystic fibrosis, no studies have been done to validate its use in COPD. Our protocol involves in-hospital patient training with the device followed by serial measurements at home in the first 30 days post hospital-discharge.

Demonstration in a pilot, single-center trial of the usefulness of real-time, repeated hand-held spirometry to provide objective measurements of lung function in AECOPD will have a substantial impact on both patient health outcomes and on health care utilization and will set the stage for appropriate next-step studies and NIH grant applications. It is unknown whether this specific technology will be acceptable in our population, though previous research suggests that older patients may be willing to use home monitoring technology. Our multi-disciplinary team includes providers from the Department of Medicine and the UCM COPD Readmissions Program team.

---

 Centers for Medicare & Medicaid Services. Readmissions Reduction Program. 2014. Available at: <http://www.cms.gov/Medicare/Medicare-Fee-for-Service-Payment/AcuteInpatientPPS/Readmissions-Reduction-Program.html>. Accessed January 14, 2015.

## PURPOSE & HYPOTHESIS

Our central hypotheses are that handheld spirometry is feasible for inpatient and at-home use and is equally efficacious at determining lung function when compared with bedside spirometry measurements. To test these hypotheses, we propose the following specific aims:

**Specific Aim 1:** Determine the correlation of SpiroPD handheld spirometry measurements with bedside Koko spirometry lung function.

**Hypothesis:** Correlation between the two lung function tests will be substantial for both hospitalized and ambulatory patients.

**Specific Aim 2:** To determine the feasibility, adherence, and preliminary management efficacy of home SpiroPD testing.

**Hypotheses:** (1) Patients will demonstrate substantial adherence to daily home spirometry testing; (2) medication adherence will increase significantly in patients who are adherent to daily home spirometry testing; (3) acute care utilization will decrease significantly in adherent patients.

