## METHODS OVERVIEW

We will enroll patients diagnosed with COPD both in the hospital and clinic setting and follow for 30 days. Participants will complete comparative lung function measurements with both devices while in the hospital or clinic at time of enrollment and at the 30-day follow up visit. Correlation will be assessed using Spearman's correlation coefficient. A high correlation ( $> 0.8$ ) will demonstrate the usefulness of the SpiroPD device in these patients in both settings. We will use the FDA-cleared (K 103575) SpiroPD device for its intended use.

At the time of their initial study visit, study participants will be given a SpiroPD device for use at home following instruction in the hospital or clinic. Patient adherence to daily testing over one-month will be monitored using real-time capture Wi-Fi-data from the SpiroPD data portal. Participant surveys will ascertain barriers and facilitators of daily spirometry lung function testing, and subject attitudes and beliefs about the usefulness of this testing for self-management. Adherence to medication use and utilization outcomes will be measured using patient logs. Acute care utilization will be measured via tracking of ED visits, hospitalizations, and urgent care calls. Information will be collected at the 30 day (+/- 1 week) visit through in-person (preferred) or phone call visits (if do not show for in person visit).

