## **Medical Record and Administrative Data Collection**

The following data will be collected by the CRDW and merged with survey and device data:

- Admission labs (e.g., bicarbonate, hemoglobin, creatinine) (hospitalized patients)
- Admission and discharge medications, inpatient medications (hospitalized patients)
- Admission length of stay (hospitalized patients)
- Admit and discharge service (hospitalized patients)
- Procedures during hospital stay (ICD-10 coded procedure) (hospitalized patients)
- Index admission type (urgent or emergent vs elective) (hospitalized patients)
- Comorbidities, ICD-9 & ICD-10
- Number of ED visits in the 12 months prior to enrollment and during the study period
- Number of hospitalizations in the 12 months prior to enrollment and during the study period
- Number and type of outpatient visits in the 12 months prior to enrollment and during the study period

- Number of observation stays in the 12 months prior to enrollment and during the study period
- PFTs
- Prescriptions for medications
- EPIC Healthy Planet data, including follow up phone calls, medication education, etc
- Consults received
- Insurance types
- Cost accounting system data (eSimon) including expected pay, net expected pay, etc.

These data will be collected from the time of electronic medical record initiation at University of Chicago (11/1/2008) until 90 days past enrollment.

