## STATISTICAL ANALYSES

**SA1:** Correlation between KoKo and SpiroPD measurements will be assessed using Spearman's correlation coefficient. A high correlation ( $> 0.8$ ) will demonstrate the usefulness of the SpiroPD device in these patients.

**SA2:** Feasibility process measures such as proportion of participants who adhere to the at-home use of SpiroPD lung function testing, adherence measures to treatment regimens, and estimates of efficacy as denoted by exacerbations and acute care utilization will be analyzed using descriptive statistics. Patient characteristic associated with increased SpiroPD use, treatment adherence, and efficacy of lung function testing will use McNemars, Fishers exact or Chi square testing for categorical variables and rank sum or t-tests for continuous variables.

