## POTENTIAL RISKS AND BENEFITS

The subject may be uncomfortable answering some interview questions. All subjects will be told that they can refuse to answer any question.

Loss of confidentiality. To help ensure that patients' health information remains private, we will restrict access to data collected for our study to study personnel only (via use of password-protection and locked cabinets for study documents). Study ID numbers will be generated and will be used when discussing and/or reviewing data at study meetings. Also, study reports will report results in aggregate and not contain information that can be used to identify individual patients.

Spirometry is safe and is commonly used to measure disease severity but can cause some minor chest soreness or lightheadedness.

You may not understand the data you see on your Spiro PD device. Use your best clinical judgement and care for your COPD as you normally would. Our research team is always available if you're not feeling well and would like to speak with a member of our COPD team.

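### Aim 2's efficacy hypotheses name no comparator, so neither an adherent/non-adherent difference nor a before/after change can be attributed to SpiroPD

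*Combined protocol and SAP*

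**What the plan says.** The objective of Specific Aim 2 (PURPOSE & HYPOTHESIS) is "To determine the feasibility, adherence, and preliminary management efficacy of home SpiroPD testing". Its hypothesis (2) expects medication adherence to rise significantly in patients who keep up daily home testing. The next reads "3) acute care utilization will decrease significantly in adherent patients". Neither names a reference group or a reference period.

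METHODS OVERVIEW describes a single group: "study participants will be given a SpiroPD device for use at home following instruction in the hospital or clinic". COMPENSATION confirms that participants keep the device. Exposure and outcome are both observed during follow-up: "Patient adherence to daily testing over one-month will be monitored using real-time capture Wi-Fi-data from the SpiroPD data portal", and "Acute care utilization will be measured via tracking of ED visits, hospitalizations, and urgent care calls". No cut-off for adherence is given.

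Under STATISTICAL ANALYSES, SA2 says that "estimates of efficacy as denoted by exacerbations and acute care utilization will be analyzed using descriptive statistics". It then lists McNemar, Fisher, chi-square, rank-sum and t-tests for characteristics associated with device use, treatment adherence and efficacy. It mentions no covariate and no stratification by enrollment setting.

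Medical Record and Administrative Data Collection provides for utilization in the 12 months before enrollment and during the study. DATA SHARING lists pre/post utilization for the final report.

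**The concern.** The hypotheses are worded as effects of testing, but the design has no group without the device. Two contrasts are available. One sets adherent against non-adherent patients, who select themselves after enrollment. The other is a change over time within adherent patients, which has nothing to separate the device from whatever else changed. SA2 does not say which is meant and plans no adjustment for either.

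If the plan is followed as written, a lower acute-care rate in adherent patients, or a fall from the prior year, could be reported as preliminary management efficacy when it reflects who adheres, where they were recruited, or how the windows are drawn. BACKGROUND says the pilot is to support next-step studies and grant applications, so a false signal would be carried forward.

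**Working it through.** **1. The plan's own figure.** There is none for Aim 2. The only sample-size table (after Exclusion Criteria) serves the Aim 1 correlation. With N = ((z0.975 + z0.80)/atanh(r))² + 3, r = 0.23 gives ((1.960 + 0.842)/0.2342)² + 3 = 146.1, against 145.92 printed. The other rows give 193.97, 123.32 and 84.93, against 193.78, 123.13 and 84.75. The table reproduces as two-sided but has no bearing on Aim 2, for which no event rate, adherent share or effect size is given. Everything below rests on assumed values, with the device effect set to zero.

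**2. Adherent versus non-adherent, mixture of risks.** Take two kinds of patient with shares w, adherence a and event rate e. The rate in adherent patients is Σwae/Σwa. In non-adherent patients it is Σw(1−a)e/Σw(1−a). With half low-risk, half high-risk and 60% adherent overall:

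| Event rate, low/high risk | Adherence, low/high risk | Adherent | Non-adherent | Ratio |
|---|---|---|---|---|
| 15% / 25% | 80% / 40% | (0.060+0.050)/0.6 = 18.3% | (0.015+0.075)/0.4 = 22.5% | 0.81 |
| 10% / 30% | 80% / 40% | (0.040+0.060)/0.6 = 16.7% | (0.010+0.090)/0.4 = 25.0% | 0.67 |
| 10% / 30% | 60% / 60% | 20.0% | 20.0% | 1.00 |
| 15% / 25% | 40% / 80% | (0.030+0.100)/0.6 = 21.7% | (0.045+0.025)/0.4 = 17.5% | 1.24 |

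The upper figure is not a bound. Reversing the wider split (10%/30%, adherence 40%/80%) gives (0.020+0.120)/0.6 = 23.3% against (0.030+0.030)/0.4 = 15.0%, ratio 1.56. With 90 adherent and 60 non-adherent patients, the chance of p<0.05 is about 24% in the 0.67 case and about 9% in the 0.81 and 1.24 cases.

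**3. Enrollment setting alone.** Assume equal numbers, event rates of 25% (inpatient) and 8% (clinic), and adherence of 50% and 70%. Adherent: (0.0625 + 0.0280)/0.6 = 15.1%. Non-adherent: (0.0625 + 0.0120)/0.4 = 18.6%. The ratio is 0.81, with about an 8% chance of p<0.05. Within each setting the ratio is 1.00, so stratification removes this part.

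**4. Shared window.** Assume that everyone has equal risk and care, that adherence means testing on at least 24 of 30 days, and that days in hospital are lost to testing and count against the patient. Daily testing propensity was drawn from Beta(8,2). With 15% to 25% admitted, the simulated ratio is 0.43 to 0.47 for a mean stay of 3 days and 0.20 to 0.23 for 5 days. At 20% and 5 days the rates are 7.3% and 33.9%, and Fisher's exact test is significant in about 99% of simulated trials of 150. The plan does not say how hospital days are counted, so this is conditional.

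**5. Before/after.** The plan does not say whether an inpatient's index admission counts in the prior 12 months. If it does, and the true rate is constant at λ per year with inpatient share s, the prior-year count is λ + s and the apparent change is λ/(λ + s) − 1.

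| Inpatient share | λ = 0.5 | λ = 1 | λ = 2 |
|---|---|---|---|
| 0.5 | −50% | −33% | −20% |
| 1.0 | −67% | −50% | −33% |

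This assumes that both periods are put on a yearly scale. The plan does not say that they are.

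**The case against.** The strongest reply is that this is a single-center pilot that calls itself observational. Aim 2 says preliminary, efficacy comes after feasibility and adherence, and SA2 keeps utilization descriptive. No decision rule hangs on it, and lacking a control arm is a choice of scope. That stands: a reader who infers a confirmatory efficacy claim goes further than the text. What remains is that a prediction of significant change in a self-selected subgroup does not fit a descriptive analysis with no named comparison.

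It can also be said that increase and decrease naturally mean change over time, and that the plan collects MARS at enrollment and at 30 days, collects prior utilization, and lists a paired test. That is a fair reading, but step 5 shows that it does not yield an attributable effect either.

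Three stronger readings are tempting and are not supported:

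- **Adherent patients receive different background COPD care.** Texting and Phone Calls shows that some patients have seen the COPD nurses, but nothing links this to adherence. The item "EPIC Healthy Planet data, including follow up phone calls, medication education, etc" is limited neither to inpatients nor to the COPD program.
- **A lower rate in adherent patients is to be expected.** Selection alone can push the ratio either way (step 2). If program care is protective and goes mainly to inpatients, and inpatients adhere less, it would pull the contrast toward no difference or reverse it.
- **No pathway to benefit exists,** because participants are told "Use your best clinical judgement and care for your COPD as you normally would". That is a caution in the risk section. Participants can see their results, and the surveys ask about usefulness for self-management.

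**Conclusion.** The point holds in this form: with no comparator named, the device given to all, adherence self-selected over the outcome window and no adjustment planned, neither available contrast can be credited to SpiroPD. A lower acute-care rate in adherent patients can arise with a null device, but the documents do not settle its size or direction. Selection alone gave 0.67 to 1.24 in the first set of mixtures, and 1.56 with the wider split reversed. Setting alone gave 0.81. The chance of a nominally significant result from selection or setting was modest, about 8% to 24%. The shared window could produce a much larger artefact, but only if hospital days count against adherence. The before/after bias depends on whether the index admission is counted. The structural conclusion needs none of these assumptions; the figures need all of them. This should be changed before analysis, but it does not undermine Aim 1 or the feasibility part of Aim 2.

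**What to change.** In PURPOSE & HYPOTHESIS and in SA2:

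- Restate hypotheses (2) and (3) as exploratory associations between SpiroPD use and each outcome, with the comparison named. Remove efficacy and management efficacy from what the study can conclude.
- Estimate each association stratified by enrollment setting. Adjust for a small set of data already collected: baseline MARS for medication adherence; prior 12-month utilization, excluding the index admission, and FEV1 from baseline spirometry for acute care use.
- Tabulate COPD-program exposure by level of SpiroPD use, descriptively only. Re-estimating within exposed and unexposed inpatients is not worthwhile: 75 × 25% is about 19 events, or roughly 9 in each half.
- State that baseline adjustment does not remove bias from admissions that reduce device use in the same 30 days.

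The cost is revised wording and one small model per outcome, with no new data. On the step 3 rates, about 19 inpatient and 75 × 8% = 6 clinic events are available. The setting-specific results should therefore be combined into one estimate and the covariates kept to those listed. The adjusted estimates will be less precise, and the study gives up an efficacy claim. A concurrent untreated group would not rescue that claim at this size: 20% versus 10% needs 199 per arm for 80% power (two-sided 0.05), and 75 per arm gives about 40%.

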## METHODS OVERVIEW

We will enroll patients diagnosed with COPD both in the hospital and clinic setting and follow for 30 days. Participants will complete comparative lung function measurements with both devices while in the hospital or clinic at time of enrollment and at the 30-day follow up visit. Correlation will be assessed using Spearman's correlation coefficient. A high correlation ( $> 0.8$ ) will demonstrate the usefulness of the SpiroPD device in these patients in both settings. We will use the FDA-cleared (K 103575) SpiroPD device for its intended use.

At the time of their initial study visit, study participants will be given a SpiroPD device for use at home following instruction in the hospital or clinic. Patient adherence to daily testing over one-month will be monitored using real-time capture Wi-Fi-data from the SpiroPD data portal. Participant surveys will ascertain barriers and facilitators of daily spirometry lung function testing, and subject attitudes and beliefs about the usefulness of this testing for self-management. Adherence to medication use and utilization outcomes will be measured using patient logs. Acute care utilization will be measured via tracking of ED visits, hospitalizations, and urgent care calls. Information will be collected at the 30 day (+/- 1 week) visit through in-person (preferred) or phone call visits (if do not show for in person visit).

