### **V0**

A trained research assistant will screen potentially eligible patient's in-person to see if they further qualify to participate. Every patient will be asked if they have access to wireless internet at home and their vision will be tested. A patient must be able to see at least 20/50 in one eye to be eligible to participate.

- Vision Assessment with Snellen Chart
  - o Chart should be two chart lengths away from participant
  - o Ask participant to cover their right eye and use their left eye to read the smallest line they can from the chart
  - o Ask participant to cover their left eye and read the smallest line they can with their right eye
  - o Administrator should follow patient's reading on a copy of the chart included in forms
  - o Record acuity in right and left eyes
  - o If vision is not better than 20/50 in at least one eye, the patient is ineligible to participate in the study.

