### **Study Schema**

	Screening V0	Baseline (in person)	Ongoing (30d)	30d Follow-Up (in-person or phone call)	90d Post- Enrollment
Informed Consent	X				
Vision Assessment	X				
Participant Data Collection:					
Self-reported demographics		X			
Self-reported health care utilization		X		X	
Respiratory symptoms/morbidity		X		X	
Quality of Life		X		X	

Health Literacy Assessment		X			
Spirometry		X		X	
SpiroPD device education		X			
SpiroPD use survey		X		X	
Reminder Text/Phone calls			X		
Device Data Collection			X		
Medical Record Data Collection		X	X	X	X

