### Texting and Phone Calls

A trained research assistant will use a study specific cell phone to communicate with patients. Patients will only be contacted by phone or text if they have given research staff permission during enrollment and provide the number to call and/or text. Patients will be able to call us directly if they need additional assistance with the device or have any questions. In addition, if the patient had been seen by our COPD APNs in the hospital and make us aware that he or she is not feeling well the research assistant will get in touch with the APN from our COPD program to ensure this information gets communicated to them. We will reach out to patients to offer additional technical support (at 7 days) and to remind them of their 30 day follow up (prior to their appointment). Patient phone numbers will be stored in the phone using a study ID number. We will not store any other identifiable information in the cell phone..

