### Device Data Collection

The SpiroPD device will record participant use and lung function scores. These measurements are stored in a HIPAA compliant server over wifi and are available to the participant and research team.

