### Survey Data Collection

Trained research staff will assess the following at the initial enrollment, post-discharge follow-up visit (for hospitalized patients), and at the 30-day follow-up:

- Demographics
- Self-reported health care utilization
- respiratory symptoms/morbidity
  - o Modified Borg Dyspnea Scale
  - o Modified Medical Research Council (MMRC) Dyspnea Scale
  - o COPD Assessment Tool
- Self-reported medication adherence
  - o MARS
- Quality of Life
  - o St. George's Respiratory Questionnaire-COPD
- Health Literacy: Ask brief health literacy screen questions for all participants
  - Brief Health Literacy Screen (BHLS) – three questions
    - o How often do you have problems learning about your medical condition because of difficulty understanding written information?
    - o How confident are you filling out medical forms by yourself?

- How often do you have someone help you read hospital material?
- SpiroPD use
  - SpiroPD Pre-Education Survey
  - SpiroPD Post-Education Survey
  - SpiroPD Follow-Up Survey
  -
- Assess vision with Snellen Chart
  - Chart should be two chart lengths away from participant
  - Ask participant to cover their right eye and use their left eye to read the smallest line they can from the chart
  - Ask participant to cover their left eye and read the smallest line they can with their right eye
  - Administrator should follow patient's reading on a copy of the chart included in forms
  - Record acuity in right and left eyes
  - If vision is not better than 20/40 in at least one eye attempt to correct vision with non-prescription glasses
    - 4 strengths of glasses: 2.00, 2.25, 2.75, and 3.25
    - Start with 2.00, and repeat the vision screen, with each eye separately
    - If visual acuity of 20/40 is reached in at least one eye, the patient is eligible to complete the STOHFLA HL evaluation using the readers
  - If vision is not corrected after trying all of the strengths of the readers, the patient is ineligible to complete the STOHFLA HL evaluation

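### Home-testing adherence is taken only from Wi-Fi portal data, and no step retrieves untransmitted tests or uses the day-7 and day-30 contacts to tell upload failure from non-use

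*Combined protocol and SAP*

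**What the plan says.** All references are to the combined protocol and SAP.

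- **Methods Overview:** "Patient adherence to daily testing over one-month will be monitored using real-time capture Wi-Fi-data from the SpiroPD data portal". This is the only stated source for the number of home tests. Patient logs are named for medication use and utilization, not for testing.
- **Device Data Collection:** "The SpiroPD device will record participant use and lung function scores". The next sentence gives the transfer route: "These measurements are stored in a HIPAA compliant server over wifi and are available to the participant and research team". Whether the device keeps unsent tests, or sends them when a connection returns, is not stated.
- **V0:** "Every patient will be asked if they have access to wireless internet at home". Home access is also an inclusion criterion. No trial upload from the home network is described.
- **Study Schema:** the row "Device Data Collection" has one mark, which reads as falling under the ongoing 30-day column and not under the 30-day follow-up. The row "SpiroPD use survey" is marked at baseline and at the 30-day follow-up.
- **Survey Data Collection:** lists a "SpiroPD Follow-Up Survey". Its items are not shown. The Methods Overview says surveys will cover barriers to and facilitators of daily testing.
- **Texting and Phone Calls:** "We will reach out to patients to offer additional technical support (at 7 days", with a further contact to remind participants of the 30-day follow-up. Contact is limited to those who gave permission. Participants may also call for help with the device.
- **Statistical Analyses, SA2:** the proportion adherent to home testing is described. No cut-off, denominator or rule for days without data is given.

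**The concern.** The device's record of use and the transfer over Wi-Fi are separate steps, and only the result of the second is named as the adherence measure. A participant whose home connection fails, or who stays somewhere without one, yields the same empty portal record as a participant who stopped testing. Nothing in the plan prompts staff to find out which it was, and nothing reads the participant's device at day 30.

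Three results depend on the distinction. The first Aim 2 hypothesis is about adherence to daily testing itself. The second concerns medication adherence in patients adherent to testing, and the third concerns acute care use in adherent patients, which I read as the same grouping. SA2 also looks for patient characteristics associated with SpiroPD use, so a characteristic linked to unreliable internet could look like a predictor of low use. For a feasibility pilot, a connection problem and an acceptability problem call for different next steps.

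Most gaps in an adherence definition can be closed at the analysis stage. This one cannot: if unsent tests are not retrieved and reasons are not recorded at the contacts, the analyst cannot rebuild them later.

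**Working it through.** **1. Is there a document figure to reproduce?** No. The documents give no expected adherence, cut-off or upload-failure rate, and the sample-size table concerns the correlation aim only.

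**2. Can the plan, as written, separate the two states?**

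| Place in the plan | Could it help? | Is it used for this? |
|---|---|---|
| Portal | Shows that uploads are missing | Does not show why |
| Day-7 contact | Could reveal a connection problem | A general offer of support, not tied to missing uploads |
| Day-30 Follow-Up Survey | Could record a connection problem by recall | Items not shown; no link to the adherence count |
| Device at day 30 | Could hold unsent tests | No device data collection marked; visit may be by phone |

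The means are largely in place. The links between them are missing.

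**3. How large could the effect be? Illustration on assumed inputs.** From the documents: 150 participants and 30 days of testing. Assumed: true daily testing rate p of 60%, 80% or 90%; share f of participants whose upload stops for good of 5% to 30%; the stopping day spread evenly over the 30 days; testing continues; days after the stop count as missed; nothing is recovered; cut-off of 21 of 30 days.

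Mean portal adherence = p × (1 − f/2). At p = 0.80:

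- f = 10%: 0.80 × 0.95 = 76%
- f = 20%: 0.80 × 0.90 = 72%
- f = 30%: 0.80 × 0.85 = 68%

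Share classed adherent = (1 − f) × A + f × B. Here A is the binomial probability of at least 21 tests in 30 days. B is the average, over k = 0 to 29 days with working upload, of the probability of at least 21 tests in k days. Number misclassified = 150 × f × (A − B).

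| p | A | B | f = 5% | f = 10% | f = 20% | f = 30% |
|---|---|---|---|---|---|---|
| 60% | 0.176 | 0.009 | 1.3 | 2.5 | 5.0 | 7.5 |
| 80% | 0.939 | 0.129 | 6.1 | 12.1 | 24.3 | 36.4 |
| 90% | 1.000 | 0.222 | 5.8 | 11.7 | 23.3 | 35.0 |

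Entries under f are participants misclassified out of 150. At p = 80%, the share classed adherent falls from 94% to 90%, 86%, 78% and 70%.

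**4. Direction.** Under these assumptions adherence itself can only be understated. For hypotheses 2 and 3 the direction is not fixed. If loss of upload is unrelated to outcome, true testers placed in the non-adherent group blur any difference. If a readmission takes a participant off the home network, people with acute care use move out of the adherent group, and that group looks better than it is.

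**The case against.** The best case for the plan has four parts.

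- **Safeguards exist.** Home wireless access is an entry criterion, participants are trained and can call for help, support is offered at day 7, and the team can see portal data throughout. A survey on SpiroPD use is planned at day 30, and lost Wi-Fi is the kind of barrier the surveys are meant to find. A reader might infer that nothing at day 30 can separate upload failure from non-use. The documents do not support that, because the survey items are not shown. What stands against the plan is that no link from the survey to the adherence count is stated, and that its answers rest on recall.
- **No scoring rule is given.** A reader might also infer that a day without an upload is counted as a missed test, or that a connection problem will be reported as unwillingness. Neither is stated. The plan is silent on how such days are classified.
- **Device behaviour is unknown.** If the device stores tests and sends them on reconnection, temporary outages correct themselves. If it stores nothing, a day-30 sync recovers nothing. Both points are right. They limit the value of the sync, but not of recording the reason.
- **Transmitted tests are a defensible feasibility measure** for a device whose purpose is remote reporting. That is fair, and it is why the fix keeps the portal-based result. It does not explain why uploads were missing.

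**Conclusion.** The concern holds in a limited form. The portal is the only named source for home-testing adherence, no step retrieves untransmitted tests, and neither the day-7 contact nor the day-30 survey is used to separate upload failure from non-use.

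The size cannot be established from the documents. The illustration runs from about 1 to about 36 of 150 participants misclassified, and it depends on the assumed failure rate, testing rate and cut-off, on days without uploads being counted as missed, and on no later back-fill. It shows that the effect could be negligible or material, and should not be read as an estimate.

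A reader might go further and conclude that the comparisons in hypotheses 2 and 3 will be diluted. That requires upload loss to be unrelated to outcome, which the documents do not show; the bias could run either way. This is a worthwhile low-cost improvement to data collection, not a flaw that invalidates Aim 2.

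**What to change.** 1. **Texting and Phone Calls:** check the portal before the existing day-7 contact and before the 30-day contact. For anyone with missing uploads, record whether testing stopped or the connection was lost, and from which date. At day 30, make this an item in the existing SpiroPD Follow-Up Survey.
2. **Study Schema and Device Data Collection:** add device data collection at the 30-day contact. Sync the participant's own device on clinic Wi-Fi if it is brought in, or at home during a phone visit. Ask participants to bring it. Count tests by the date of the test, not the date of upload.
3. **Statistical Analyses, SA2:** report adherence with untransmitted days counted as missed and, as a sensitivity analysis, with documented upload-failure days excluded. For example, a participant with 12 tests in 15 connected days followed by 15 documented failure days scores 12/30 = 40% in the first and 12/15 = 80% in the second.

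**Cost:** a few minutes per contact and one added form item. Recovery will be less complete for those who finish by phone, the reasons rest on recall, and participants who declined phone or text contact will be missed at day 7. If the device does not hold unsent tests, none are recovered and only the recorded reason is gained.
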